Protocol synopsis, Section 2.3 EXPLORATORY OBJECTIVES and Section 3.3.3 EXPLORATORY OUTCOME MEASURE and Section 4.6.1.8 STUDY-SPECIFIC ASSESSMENTS and Section 4.6.2 TIMING OF STUDY ASSESSMENT and Section 11 APPENDIX 1 SCHEDULE OF ASSESSMENTS	The CGI-S has been included within exploratory assessments.	As per FDA request.
Protocol synopsis, Section 3.3.1 SAFETY OUTCOME MEASURES, Section 4.6.2 TIMING OF STUDY ASSESSMENTS, Section 5.1.4 OTHER SAFETY ASSESSMENTS and Section 11 APPENDIX 1 SCHEDULE OF ASSESSMENTS	Given the risk of ototoxicity with [REDACTED], hearing assessments will be performed multiple times.	As per FDA request.
Section 1.5.2 BENEFIT-RISK ASSESSMENT and Section 4.5.1.3 MEDICATIONS TO BE AVOIDED WITH STP1.	The concomitant treatment with CYP3A4 moderate or strong inhibitors is excluded.	As per FDA request.
Protocol synopsis and Section 3.1.2 STOPPING RULES and Section 5.1.3 ADVERSE EVENTS OF SPECIAL INTEREST (IMMEDIATELY REPORTABLE TO THE SPONSOR)	Dehydration and orthostasis have been included within the adverse events of special interest.	As per FDA request.

Section # and Name	Description of Change	Brief Rationale
Section 6.7.2 OTHER EXPLORATORY ENDPOINTS.	All exploratory endpoints are now reorganized and also included in the screening process.	For clarity and comprehension. Exploratory endpoints also performed before starting treatment (in the screening period).
Protocol synopsis and Section 4.2.2 INCLUSION CRITERIA	Abstinence is not any more mentioned as an appropriate method of birth control for this study.	As per FDA request
Protocol synopsis and Section 4.2.2. INCLUSION CRITERIA	Requirement for at least a 6-month seizure free period has been added as inclusion criteria	As per FDA request
Protocol synopsis and Section 4.2.3. EXCLUSION CRITERIA	Patients with an identified genetic cause of ASD in their medical record will be excluded from the study.	As per FDA request
Section 11 APPENDIX 1 SCHEDULE OF ASSESSMENT	The suicidality assessments (C-SSRS, C-CASA) has been added to the follow-up visits.	As per FDA request
Section 4.6.1.8 STUDY-SPECIFIC ASSESSMENTS Section 11 APPENDIX 1 SCHEDULE OF ASSESSMENT	Drug accountability has been added to Day 7 and Day 14 visit	
Typos and clarifications.	New references have been added.	Minor corrections and clarifications.

Protocol Amendment 2 Summary of Changes (09 December 2020)

Section # and Name	Description of Change	Brief Rationale

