3.3 OUTCOME MEASURES

3.3.1 SAFETY OUTCOME MEASURES

The safety outcome measures for this study are as follows:

- Incidence, nature and severity of AEs.
- Incidence, nature and severity of SAEs.
- Incidence, nature and severity of AESIs.
- Incidence, nature and severity of AEs leading to treatment discontinuations.
- Changes from baseline in systolic blood pressure (SBP), diastolic blood pressure (DBP), heart rate (HR) and respiratory rate.
- Changes from baseline in orthostatic measurements of BP and HR.
- Changes from baseline in ECG parameters (HR, PQ, QRS, QT, RR and QTcF, along with information on T and U waves).
- Incidence of clinically significant ECG abnormalities.
- Hearing assessment
- Incidence of clinically relevant laboratory abnormalities, based on hematology, blood chemistry and urinalysis test results:
 - Hematology: hemoglobin, hematocrit, erythrocytes, platelet count, leucocytes differential (absolute) counts (neutrophils, eosinophils, lymphocytes, monocytes, basophils).
 - Blood chemistry: aspartate aminotransferase (AST), alanine aminotransferase (ALT), gamma-glutamyltransferase (GGT), total and conjugated bilirubin, alkaline phosphatase (ALP), albumin, creatine phosphokinase (CPK), creatinine, urea, total protein, total cholesterol, triglycerides, sodium, chloride, calcium, magnesium, phosphate, potassium, glucose.
- Incidence of value outside of the normal ranges of blood chemistry test results for electrolytes:
 - Sodium, chloride, calcium, magnesium, phosphate, potassium
- Urinalysis: protein, blood, glucose, leucocytes, nitrites, pH, and presence of crystals.

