1.1 Design and Treatment

The first dose cohort (8 eligible patients) will be randomized and allocated to one of two treatment groups using a 3:1 ratio:

- █ mg oral twice a day (BID) ibudilast █ mg oral BID bumetanide (N=6)
- Matching oral placebos BID (N=2)

For each dose cohort, the total duration of the study for each patient will be up to 6 weeks, divided as follows:

- A screening phase of up to 2 weeks (from Day -14 to Day -1)
- A double-blind treatment phase of 2 weeks (from Day 1 to Day 14)
- A follow-up phase of 2 weeks after treatment discontinuation (from Day 15 to Day 28)

Once the first cohort (8 patients) finishes 2 weeks of treatment and 2 weeks of follow-up, a Data Safety Monitoring Board (DSMB) will evaluate the safety data to decide whether the dose of ibudilast can be increased as planned to █ mg, or the study shall be modified or be stopped.

If the DSMB decision supports the start of the next dose level, up to 8 additional eligible patients will be assigned to one of the following two treatment groups (a minimum of 3 patients should be exposed to the highest dose of STP1):

[figure not shown]
- █ mg oral BID ibudilast/ 1 mg oral BID bumetanide (up to N=6)
- Matching oral placebos BID (up to N=2)

Patients that participated in the first dose cohort may be allowed to participate in

the second dose cohort if there is no safety concern and after drug washout. Any patient from Cohort 1 that is re-randomized into Cohort 2 will be counted as a new patient in the analysis. That is, re-enrolled patients will be assigned a new patient ID for Cohort 2, re-randomized, and have a new set of CRFs completed.

Figure 1 below summarizes an overview of the study design.

Figure 1. Overview of Study Design

For STP1 dose 2: N= up to 2 placebo and up to 6 STP1 dose 2, randomization is N= up to 8

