- Hearing assessment (collected for only those patients enrolled under Version 4 or subsequent versions of the protocol)
- Administration of the study medication
- Study medication supply
- Blood and urine sampling for PK
- Perform study-specific assessments: Suicidality assessment (C-SSRS or C-CASA), OACIS-Severity, NIH-CTB, KiTAP, CSHQ, and CGI-S

- OACIS-Severity and CGI-S are collected for only those patients enrolled under Version 2 or 3 of the protocol. C-SSRS is collected for only those patients enrolled under Version 4 or subsequent versions of the protocol.
- Eye tracking assessment
- EEG (pre- and post-dose)
- Adverse Events
- Previous and Concomitant treatments

Visit 3 - Day 7

- Physical examination
- Vital Signs: including temperature, HR, and respiratory rate, and BP
- Orthostatic BP assessment
- ECG-12 lead
- Blood sampling for hematology, blood chemistry, and coagulation
- Urine sampling for urinalysis
- Administration of the study medication and drug accountability
- Blood sampling for PK
- Suicidality assessment (C-SSRS or C-CASA) (C-SSRS collected for only those patients enrolled under Version 4 or subsequent versions of the protocol)
- Hearing assessment (collected for only those patients enrolled under Version 4 or subsequent versions of the protocol)
- Adverse Event
- Previous and Concomitant treatments

Visit 4 - Day 14

- Physical examination
- Vital Signs: including temperature, HR, respiratory rate, and BP
- Orthostatic BP assessment
- ECG-12 lead
- Blood sampling for hematology, blood chemistry, and coagulation
- Urine sampling for urinalysis
- Administration of the study medication and drug accountability
- Blood and urine sampling for PK
- Hearing assessment (collected for only those patients enrolled under Version 4 or subsequent versions of the protocol)
- Perform study-specific assessments: Suicidality (C-SSRS and C-CASA), ABC-C, SRS-2, OACIS-S, Ohio Autism Clinical Impression Scale - Improvement (OACIS – C),  KiTAP, CSHQ, Clinical Global Impressions – Improvement (CGI-I) Scale, and CGI-S
 - C-SSRS is collected for only those patients enrolled under Version 4 or subsequent versions of the protocol.

- Eye tracking assessment
- EEG
- Adverse Events
- Previous and Concomitant treatments

Visit 5- Day 15 and Optional Visit 6/7/8 - Days 16/17/18

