2.0 Data Analysis Considerations

2.1 Types of Analyses

For this Phase 1b study, descriptive statistics will be provided for all variables by treatment group (placebo data will be pooled from the two dose cohorts). For continuous endpoints, summary statistics, i.e., n (number of non-missing observations), mean, standard deviation (SD), median, minimum, and maximum will be provided. For categorical variables, the frequency count and proportion in each category will be summarized.

As mentioned in Section 1.2 of the SAP, some assessment time points will vary according to which protocol amendment was in place at the time a patient was enrolled. Data from all time points will be summarized as appropriate in accordance with the details provided below in Section 3 – 7.

All data collected will be presented in the by-patient data listings, sorted by patient and by time point, where appropriate.

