Shift tables will be constructed to show the changes in laboratory results in relation to clinical significance (e.g., normal, abnormal clinically significant (CS), abnormal not clinically significant (NCS)) from baseline to each visit. This analysis will be repeated for blood chemistry results for electrolytes (sodium, chloride, calcium, magnesium, phosphate, potassium).

A shift table for blood chemistry results for electrolytes will be constructed to show the changes in laboratory results in relation to range of normal results (e.g., normal, high, low) from baseline to each visit.

The count and proportion of patients with blood chemistry results for electrolytes outside of the normal range (low, high) for each visit will be summarized by treatment and overall.

All laboratory results data will be provided in data listings as shown in Appendix B.

Hearing Assessment

The patient responses to the hearing assessment for each visit will be listed as shown in Appendix B.

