$AUC_{0-\infty}$	Area under the plasma concentration time curve extrapolated to infinity, calculated as $AUC_{0-last} + C_{Last}/\lambda_z$
V_z/F	Apparent volume of distribution
Cl/F	Apparent total body clearance
Accumulation Ratio	Ratio of accumulation of a drug, calculated by the following equation: $AR_{AUC} = AUC_{0-tau (6h), SS} / AUC_{0-tau (6h), Day 1}$ $AR_{Cmax} = C_{max,ss} / C_{max, Day 1}$

As the PK time schedules were different prior to the implementation of Version 4.0 (Amendment 3) of the clinical study protocol, the PK schedule of the first 4 patients is as follows:

Day 1

- Blood sampling at pre-AM dose and 0.25, 0.5, 1, 2, 4, 6 h post-AM dose
- Urine sampling at 0 to 6 h post-AM dose

Day 7

- Blood sampling at pre-AM dose

Day 14

- Blood sampling at pre-AM dose and 0.25, 0.5, 1, 2, 4, 6, 8, 10, 24 and 30 h post-AM dose
- Urine sampling 0 to 6 h and 24 to 30 h post-AM dose

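### Hearing assessment is a primary safety endpoint, but the SAP gives it no by-group summary and no assessed denominator, although the first 4 patients were by design never given it

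*SAP*

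**What the plan says.** **Status of the endpoint.** The protocol synopsis places hearing among the primary safety endpoints, and Protocol 3.3.1 lists "Hearing assessment" as a safety outcome measure. SAP 4.1 names it as a safety variable. The Amendment 3 summary of changes gives ototoxicity risk as the reason and states that "hearing assessments will be performed multiple times".

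**Who has it.** SAP 1.2 attaches the same restriction at Days 1, 7, 14 and 28: "Hearing assessment (collected for only those patients enrolled under Version 4 or subsequent versions of the protocol". SAP 5.1 describes a PK schedule that applied "prior to the implementation of Version 4.0 (Amendment 3) of the clinical study protocol" and says that "the PK schedule of the first 4 patients is as follows".

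**What is produced.** SAP 2.1 says that "descriptive statistics will be provided for all variables by treatment group", with counts and proportions for categorical variables; the synopsis makes the same promise for all endpoints. For hearing, SAP 4.2 provides one sentence: "The patient responses to the hearing assessment for each visit will be listed as shown in Appendix B". The shell (Listing 12) has one yes/no item on hearing change since the previous visit, plus a free-text explanation, under a Safety population heading. None of the 50 tables in SAP 8.0 covers hearing. Appendix A prints all missing values as blanks.

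**The concern.** A primary safety endpoint that was added for a named risk will have no count by treatment group. It was also collected unequally: by the SAP's own rules, half of planned Cohort 1 was never asked the scheduled question, while anyone in Cohort 2 is asked at every hearing visit. Nothing in the outputs separates a blank that is structural (enrolled before Version 4) from one that is an ordinary missing answer.

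At stake is how an absence of hearing findings at the lower dose will be read. A reader who sees an empty or all-no listing headed with the Safety population size may take it as evidence from every patient in the group. If a hearing table were added later on the SAP's usual footnote, which divides by all Safety patients in the group, the denominator would be wrong for this item.

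**Working it through.** **1. Planned numbers.** SAP 1.3: up to 16 evaluable patients with about 20% dropout gives 16 / (1 − 0.20) = 20, which matches the stated maximum. For Cohort 1, SAP 1.1 says: "The first dose cohort (8 eligible patients) will be randomized and allocated to one of two treatment groups using a 3:1 ratio". That is 6 active and 2 placebo.

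**2. Who precedes Version 4.** SAP 5.1 equates Version 4.0 with Amendment 3 and gives 4 patients on the older PK schedule. SAP 1.2 assigns a 30-hour sample to Version 2 or 3 patients, and that sample is in the schedule of those 4, so the cut-off is the same one used for hearing. Cohort 1 must finish treatment and follow-up before Cohort 2 can open, so all 4 are in Cohort 1.

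- Cohort 1 assessed: 8 − 4 = 4 of 8 (50%)
- Full planned study assessed: 16 − 4 = 12 of 16 (75%)

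**3. Split by arm.** The synopsis specifies permuted blocks at 3:1 but no block size. Two assumptions deliver 6:2 in 8 patients.

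- *Blocks of 4:* the first 4 are 3 active and 1 placebo. Assessed: 3 of 6 lower-dose and 3 of 4 pooled placebo.
- *One block of 8:* P(a active among the first 4) = C(6,a) × C(2,4−a) / C(8,4), with C(8,4) = 70.

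| Active among first 4 | Probability | Lower-dose assessed (of 6) | Pooled placebo assessed (of 4) |
|---|---|---|---|
| 2 | 15/70 = 0.21 | 4 | 2 |
| 3 | 40/70 = 0.57 | 3 | 3 |
| 4 | 15/70 = 0.21 | 2 | 4 |

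**4. Rate on the scheduled question.** One yes answer in the lower-dose group is 1/6 = 17% on the Safety count, but 1/3 = 33% of those asked (range 1/4 = 25% to 1/2 = 50%).

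**5. What a zero count would exclude (worst case).** This step assumes that the scheduled question is the only way a hearing change is found. The one-sided 95% upper bound with no events is 1 − 0.05^(1/n). The last column uses an assumed true rate of 20%, which the documents do not give: 1 − 0.8^n.

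| n | Upper bound at 0/n | Chance of at least one case at 20% |
|---|---|---|
| 6 | 39% | 74% |
| 4 | 53% | 59% |
| 3 | 63% | 49% |
| 2 | 78% | 36% |

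**The case against.** The strongest reply is that the SAP divides nothing by 6. It plans a listing, and with at most about 20 patients a reader can see who answered. SAP 2.3 already says that only observed data are used. SAP 2.1 defers to Sections 3 to 7 for data that vary by amendment, and Section 4.2 is that detail. Physical examination and suicidality are also listing-only. The plan is descriptive, with confidence intervals only for PK, and six patients settle nothing about ototoxicity either way.

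Part of this stands: no wrong hearing rate is built into any output. A reader might infer that hearing terms in the AE tables are divided by too many patients. The documents do not support that. AEs are sought at every contact by open questions (Protocol 5.3.1 and 5.3.2) with no version restriction, so an unassessed patient could still report a hearing change and belongs in the AE denominator. Nor do the documents support the inference that the lower-dose group must look safer than it is. Pooled placebo probably has unassessed patients too, the split of the first 4 is unknown, and detection in unassessed patients is not zero.

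The rest does not remove the point. Physical examination and suicidality are not in the protocol's list of primary safety endpoints; hearing is. The SAP writes version-specific handling for PK (5.1) and CGI (6.2), so its absence for hearing is a specific gap. Blanks in a listing do not say why they are blank.

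**Conclusion.** The point holds as a gap in reporting and unequal ascertainment. A primary safety endpoint lacks its promised by-group summary, and its proper denominator, patients actually assessed, is defined nowhere. By plan that denominator is 4 of 8 in Cohort 1 and 12 of 16 overall. In the worst case of step 5 the informative lower-dose n is 2 to 4 rather than 6, and the zero-count bound is 53% to 78% rather than 39%. Because open AE questioning reaches everyone, the true position lies between these extremes.

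This rests on four assumptions:

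- The count of 4 is stated for PK and carried to hearing through the shared version cut-off.
- Block size is unstated, so per-arm figures are ranges.
- Replacements could take Cohort 1 above 8, so 50% is the planned share.
- A Cohort 1 patient who re-enters in Cohort 2 would be assessed there, but SAP 1.1 counts that as a new patient.

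**What to change.** Add one table to SAP 4.2, by treatment group:

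- *Numerator:* patients with any post-dose yes (Days 7, 14 or 28) to the hearing-change item in Listing 12.
- *Denominator:* patients with at least one post-dose hearing assessment.
- *Separate line:* not assessed (enrolled before Version 4), with its count.

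Mark the same patients as not assessed in Listing 12 instead of leaving blanks. Leave the AE-table denominators unchanged; note only that the directed hearing question was not put to patients enrolled before Version 4. State the uncollected data as a limitation, since they cannot be recovered.

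The cost is one small table from data already collected, and a visibly smaller lower-dose n. No clinical procedure changes.

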5.0 Analysis of Pharmacokinetics

5.1 Description of Pharmacokinetic Variables

PK sampling will be collected from all patients for measurement of plasma and urine concentrations of ibudilast and bumetanide.

Blood samples will be drawn on Days 1, 7, 14/15 and, optionally, between Days 16 to 18, and urine samples will be collected on Days 1 and 14 to determine concentrations of ibudilast and bumetanide. Non-compartmental analysis (NCA) will be utilized to analyze data from the sampling schema. See Table 1 for the PK sample schedule.

Table 1. PK Sampling Schedule

PK Schedule ^c		
Time	Plasma ^a	Urine ^b
Day 1	0.25, 0.5, 1, 2, 4, and 6h post-AM dose	0 to 6h post-AM dose
Day 7	Pre-AM dose	
Day 14 (only AM dose) and 15	Pre-AM dose and 0.25, 0.5, 1, 2, 4, 6, 8, 10, 12 and 24h post-AM dose	0 to 4h, 4 to 8h, and 8-12h post-AM dose
Between Days 16 to 18 ^d	48, 72, and 96 h post-AM dose of Day 14	

^a Both ibudilast and bumetanide will be analyzed from the same blood draw for each specified sampling time point.
^b Urine creatinine from the urine collection will be paired with a serum creatinine measurement to evaluate completeness of collection.
^c All of these timepoints have a 5-minute window.
^d Optional

The following PK plasma parameters will be estimated for each patient(as far as possible):

PK Parameter	Definition
$C_{max, Day 1}$	Maximum plasma concentration on Day 1
$C_{max,ss}$	Maximum plasma concentration at steady state
C_{Last}	Last measured plasma concentration following the last administration
C_{trough}	Minimum observed plasma concentration prior to drug administration
T_{max}	Time of maximum observed plasma concentration; if it occurs at more than one time point, T_{max} is defined as the first time point with this value
$t_{1/2}$	Terminal elimination half-life, calculated as $\ln(2)/\lambda_z$
AUC_{0-last}	Cumulative area under the plasma concentration time curve calculated from 0 to the last measured plasma concentration following the last administration using the linear trapezoidal method
$AUC_{0-tau (6h), Day 1}$	Area under the plasma concentration time curve to the end of the dosing period following the first administration
$AUC_{0-tau (6h), SS}$	Area under the plasma concentration time curve to the end of the dosing period (6h) following the last administration
$AUC_{0-12h, SS}$	Area under the plasma concentration time curve to 12 hours post dose following the last administration
$AUC_{0-\infty}$	Area under the plasma concentration time curve extrapolated to infinity, calculated as $AUC_{0-last} + C_{Last}/\lambda_z$
V_z/F	Apparent volume of distribution
Cl/F	Apparent total body clearance
Accumulation Ratio	Ratio of accumulation of a drug, calculated by the following equation: $AR_{AUC} = AUC_{0-tau (6h), SS} / AUC_{0-tau (6h), Day 1}$ $AR_{Cmax} = C_{max,ss} / C_{max, Day 1}$

As the PK time schedules were different prior to the implementation of Version 4.0 (Amendment 3) of the clinical study protocol, the PK schedule of the first 4 patients is as follows:

Day 1

- Blood sampling at pre-AM dose and 0.25, 0.5, 1, 2, 4, 6 h post-AM dose
- Urine sampling at 0 to 6 h post-AM dose

Day 7

- Blood sampling at pre-AM dose

Day 14

- Blood sampling at pre-AM dose and 0.25, 0.5, 1, 2, 4, 6, 8, 10, 24 and 30 h post-AM dose
- Urine sampling 0 to 6 h and 24 to 30 h post-AM dose

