5.2 Analysis of Pharmacokinetic Variables

Plasma and urine sample concentrations of ibudilast and bumetanide will be summarized by treatment, visit and time point using descriptive statistics.

Individual plasma concentrations of ibudilast and bumetanide will be depicted for each patient by treatment group using linear scale. Individual and mean plasma concentration- time profiles will be plotted in linear and semi-logarithmic scales.

PK parameter values will be summarized by treatment group using descriptive statistics (n, mean, SD, CV%, geometric mean, and 90% confidence interval). Plasma PK parameters such as $AUC_{0-\tau}$, AUC_{last} , C_{max} , T_{max} , C_{trough} , apparent oral clearance, the elimination half-life, apparent volume of distribution and accumulation ratios will be calculated following single dose administration (as far as possible) and at steady state for both parent drugs.

Urine parameters include the following:

- Excretion rate by timepoint:
 - Day 1, 0-6h
 - Day 14, 0-4h
 - Day 14, 4-8h
 - Day 14, 8-12h
- Cumulative excretion, based on Day 14 sampling over 0-12h
- Renal clearance, based on Day 14 sampling over 0-12h

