Statistical Analysis Plan

STP1-C004

Table 32. Summary Statistics of Ibudilast and Bumetanide Plasma Concentration Levels by Treatment, Visit, and Time
 STALICIA SA - Study No. STPL-C004
 PK Population (N=xxx)

Concentration levels measured in units of xxx
STATKING Clinical Services (month day, year)
Source Program: xxxxxxx.sas

Statistical Analysis Plan

STP1-C004

Table 33. Summary Statistics of Ibudilast and Bumetanide Urine Concentration Levels by Treatment, Visit and Time
STALICIA SA - Study No. STP1-C004
PK Population (N=xxx)

Concentration levels measured in units of XXX.
STATKING Clinical Services (month day, year)
Source Program: xxxxxxx.sas

Statistical Analysis Plan

STP1-C004

Table 34. Summary Statistics of Estimated PK Plasma Parameters for Ibudilast by Treatment

PK Population (N=xxxx)

Part 1 of 2: STP1-  ibudilast

Page x of y

Visit	Parameter (units)	n	Mean	Std Dev	CV%	Geometric Mean	Lower 90% CI	Upper 90% CI
Day 1								
	$C_{max,day\ 1}$ (xxx/mL)	xxx	xxx	xxx	xxx	xxx	xxx	xxx
	T_{max} (hrs)	xxx	xxx	xxx	xxx	xxx	xxx	xxx
	$C_{through}$ (xxx /mL)	xxx	xxx	xxx	xxx	xxx	xxx	xxx
	$t_{1/2}$ (hrs)	xxx	xxx	xxx	xxx	xxx	xxx	xxx
	$AUC_{0-\tauau(6h), day\ 1}$ (hrs* xxx/mL)	xxx	xxx	xxx	xxx	xxx	xxx	xxx
	$AUC_{0-\text{last}}$ (hrs* xxx/mL)	xxx	xxx	xxx	xxx	xxx	xxx	xxx
	Vz/F (mL)	xxx	xxx	xxx	xxx	xxx	xxx	xxx
	CL/F (mL/hrs)	xxx	xxx	xxx	xxx	xxx	xxx	xxx
Day 14								
	$C_{max,ss}$ (xxx /mL)	xxx	xxx	xxx	xxx	xxx	xxx	xxx
	T_{max} (hrs)	xxx	xxx	xxx	xxx	xxx	xxx	xxx
	$C_{through}$ (xxx /mL)	xxx	xxx	xxx	xxx	xxx	xxx	xxx
	$t_{1/2}$ (hrs)	xxx	xxx	xxx	xxx	xxx	xxx	xxx
	$AUC_{0-\tauau(6h),ss}$ (hrs* xxx/mL)	xxx	xxx	xxx	xxx	xxx	xxx	xxx
	$AUC_{0-12h,ss}$ (hrs* xxx/mL)	xxx	xxx	xxx	xxx	xxx	xxx	xxx
	$AUC_{0-\text{last}}$ (hrs* xxx/mL)	xxx	xxx	xxx	xxx	xxx	xxx	xxx
	Vz/F (mL)	xxx	xxx	xxx	xxx	xxx	xxx	xxx
	CL/F (mL/hrs)	xxx	xxx	xxx	xxx	xxx	xxx	xxx
Overall								
	$AUC_{0-\infty}$ (hrs* xxx/mL)	xxx	xxx	xxx	xxx	xxx	xxx	xxx
	AR_{auc}	xxx	xxx	xxx	xxx	xxx	xxx	xxx
	AR_{max}	xxx	xxx	xxx	xxx	xxx	xxx	xxx

STATKING Clinical Services (month day, year)
Source Program: xxxxxxxx.sas

Statistical Analysis Plan

STP1-C004

Table 34. Summary Statistics of Estimated PK Plasma Parameters for Ibudilast by Treatment

STALICLA SA – Study No. STP1-C004
PK Population (N=xxx)

Part 2 of 2: STP1-~~X~~ng ibudilast

Visit	Parameter (units)	n	Mean	Std Dev	CV%	Geometric Mean	Lower 90% CI	Upper 90% CI
Day 1								
	$C_{max, day 1}$ (xxx/mL)	xxx	xxx	xxx	xxx	xxx	xxx	xxx
	T_{max} (hrs)	xxx	xxx	xxx	xxx	xxx	xxx	xxx

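### AUC0-last is pooled over Day 14 profiles ending anywhere from 24 h to 96 h, and ibudilast AUC0-inf is taken after the last of 27 doses, so it includes carry-over and is not comparable with a single-dose AUC0-inf

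*SAP*

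**What the plan says.** **Definitions.** In SAP 5.1, AUC0-last runs "from 0 to the last measured plasma concentration following the last administration using the linear trapezoidal method", and CLast is tied to the last dose in the same way. AUC0-inf is the "Area under the plasma concentration time curve extrapolated to infinity, calculated as" AUC0-last + CLast/lambda-z. That is the only formula given. The protocol synopsis plans AUC0-inf on Day 1 and on Day 14. Table 34 ("Summary Statistics of Estimated PK Plasma Parameters for Ibudilast by Treatment") and Table 35 print one AUC0-inf row, under Overall, and list AUC0-last under both days.

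**End times.** The current Day 14/15 schedule ends at 24 h, with optional draws at 48, 72 and 96 h. For patients before protocol Version 4, "the PK schedule of the first 4 patients is as follows", and the Day 14 line is "Blood sampling at pre-AM dose and 0.25, 0.5, 1, 2, 4, 6, 8, 10, 24 and 30 h post-AM dose". SAP 1.2 also keeps a Day 28 PK sample for Version 2 or 3 patients. SAP 1.1 says "The first dose cohort (8 eligible patients) will be randomized", so the first 4 patients are all in cohort 1.

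**Summaries.** SAP 5.2 says "PK parameter values will be summarized by treatment group using descriptive statistics" and makes no split by sampling schedule.

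**Clearance.** Cl/F is listed only as "Apparent total body clearance", without a formula, and Vz/F likewise. Protocol 3.3.2 places both at steady state. SAP 5.1 also defines two fixed-window areas after the last dose, AUC0-tau(6h),SS and AUC0-12h,SS.

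**The concern.** Two summarised areas do not measure what their names suggest for ibudilast. AUC0-last depends on when sampling stopped, and that differs by cohort and by who accepts the optional draws. AUC0-inf after dose 27 contains drug left from the 26 earlier doses, and no label says so.

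Protocol 3.2.3 says the PK data will be compared with the literature, examined against adverse event incidence, and used to help identify Phase 2 dose levels. Protocol 1.4.1 offers the natural comparators: a single-dose AUC0-inf, and an expected AUCtau,ss of at most 170 ng.h/mL. An area set beside the wrong comparator would misstate exposure, and a dose-level difference in AUC0-last could come from sampling alone.

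**Working it through.** **1. Inputs.** Days 1-13 twice daily plus one morning dose gives 13 x 2 + 1 = 27 doses (synopsis; morning-only on Day 14 is assumed here). The two daily doses are 6 h apart, so the doses before the last fall 18, 24, 42, 48 ... h earlier. Protocol 1.4.1 gives, for 30 mg ibudilast: Cmax 32 ng/mL, Tmax 4-5 h, half-life about 19 h, and AUCtau,ss 516.6 and 506.5 ng.h/mL, about 0.9 of the single-dose AUC0-inf. That implies 516.6/0.9 = 574.0 and 506.5/0.9 = 562.8.

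**2. The plan's own figure.** Scaling 30 mg to 10 mg gives 516.6/3 = 172.2 and 506.5/3 = 168.8, against the stated 170. It reproduces. (The dose is blacked out in that sentence; 10 mg is the highest study dose named in the section.)

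**3. Carry-over, simplest form.** Let a single-dose AUC0-inf = 1. With k = 0.693/19 = 0.0365 per h, exp(-18k) = 0.519 and exp(-24k) = 0.417. The residual area is (0.519 + 0.417)/(1 - 0.417) = 1.60, so AUC0-inf after the last dose is 2.60.

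**4. With absorption.** For first-order absorption the fraction still to come at time t is R(t) = (ka exp(-kt) - k exp(-ka t))/(ka - k). AUC0-inf is the sum of R over the 27 dose ages, and the area to time e is the sum of R(age) - R(age + e).

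| Curve | 0-24 h | 0-96 h | 96 h/24 h | AUC0-inf |
|---|---|---|---|---|
| One compartment, 19 h (Tmax 4.5 h, ka 0.69) | 1.55 | 2.61 | 1.69 | 2.69 |
| Biphasic, terminal 19 h (28 fits) | 1.29-1.36 | 1.71-2.04 | 1.32-1.50 | 1.73-2.09 |
| One compartment, 8.7 h (Tmax 4.5 h, ka 0.478) | 1.29 | 1.54 | 1.20 | 1.54 |

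The biphasic fits match single-dose Cmax, AUC, Tmax and terminal half-life; their first-phase half-life (1.5-8 h) is an assumption.

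**5. No row meets every stated figure.** The 19 h one-compartment curve predicts a 30 mg Cmax of about 17-18 ng/mL, not 32. The 8.7 h curve abandons the 19 h half-life. At 170 ng.h/mL per dose, the biphasic curves give a Cmax of about 15-16 ng/mL after the Day 14 dose, where Section 1.4.1 expects about 10.

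**6. Mixing with dose level.** By linear trapezoid on the biphasic curves, 30 h against 24 h is 1.10-1.12 and 96 h against 24 h is 1.36-1.52. Assume 6 active patients per dose and equal true CL/F. Cohort 1 has 2 placebo patients, so 2-4 of the first 4 are active. The dose 2/dose 1 ratio of dose-normalised geometric mean AUC0-last is then:
- no optional draws: 1/1.10^(2/6) = 0.97 to 1/1.12^(4/6) = 0.93;
- all of dose 2 and none of dose 1 take them: up to 1.52/1.12^(2/6) = 1.46;
- the reverse: down to 1/(1.12^(2/6) x 1.52^(4/6)) = 0.73.

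AUC0-24h gives 0.99.

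**7. Day 28.** This is about 336 h after the last dose, or 336/19 = 17.7 half-lives, so drug may well not be measurable. If it is, the linear trapezoid bridges 30 h to 336 h in one step.

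**8. Other areas.** On the biphasic curves the 0-6 h area is 0.461-0.497 of a per-dose area. A patient exactly at 170 would show 170 x 0.461 = 78 to 170 x 0.497 = 84. The 0-12 h area is 0.873-0.919 over all three rows, so Dose/AUC0-12h,SS overstates CL/F by 1/0.919 to 1/0.873, about 9-15%; Dose/AUC0-6h overstates it 2.0-2.2 times. A three-point lambda-z on the biphasic curves gives a half-life of 8.9-11.9 h from 24 h profiles and 18.1-19.0 h with 96 h draws.

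**9. Bumetanide.** At a half-life of 1-1.5 h, AUC0-inf is 1.000-1.004 of the single-dose value.

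**The case against.** The strongest reply is that the SAP is open about what it computes. AUC0-last is defined as following the last dose, AUC0-inf is visibly built from it, and individual parameters are listed. Two fixed-window areas, AUC0-tau(6h),SS and AUC0-12h,SS, are already tabulated, so a dose comparison need not rest on AUC0-last. PK is secondary and descriptive, and no decision rule uses these areas. The 0.73-1.46 range needs all-or-none uptake of the optional draws; with no uptake the distortion is 3-7%.

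All of that stands, and it limits the weight of the point. It does not remove it: AUC0-last remains a summarised row whose value depends on schedule, and Tables 34-35 carry no carry-over label.

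A reader might infer more than the documents support:
- **That the SAP uses the last-dose AUC0-inf as a per-dose area or for clearance.** It assigns it to neither; the error arises only if someone divides dose by it or sets it beside a single-dose value.
- **That one multiplier can be quoted.** The 19 h half-life alone suggests about 2.7, and curves fitted to the single-dose figures about 1.7-2.1. The source data are also from a delayed-release product, while the trial uses sustained-release granules.
- **That the missing Cl/F and Vz/F formulas are an error in themselves.** They are mostly missing detail, which matters because the candidate areas differ so much.

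**Conclusion.** The point holds in this form. As written, SAP 5.1 and 5.2 make the AUC0-last summary depend on sampling end time, which is tied to cohort through the first 4 patients and to individual choice through the optional draws. For the same ibudilast exposure, 96 h against 24 h is about 1.3-1.7 with a 19 h terminal half-life; the 8.7 h curve gives 1.2. Ibudilast AUC0-inf after the last dose exceeds a single-dose AUC0-inf by a factor of about 1.5-2.7.

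The direction follows from dosing 18 h and 24 h before the last dose with a half-life near 19 h. The sizes assume linear kinetics, full adherence, no afternoon dose on Day 14, and disposition carried over from another formulation; they are indicative only. Bumetanide is essentially unaffected. The change should be made before the tables are produced, but nothing here touches the primary safety objective.

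**What to change.** In SAP 5.1, 5.2 and Tables 34-35, using existing samples only:

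1. Summarise AUC0-24h after the last dose as the common-window measure. Both schedules have a 24 h sample, and on the same curve they differ by at most 2%. Move AUC0-last to the listings.
2. Place AUC0-inf under Day 14 and label the ibudilast value as including carry-over. Do not use it for CL/F or Vz/F, and do not compare it with a single-dose AUC0-inf.
3. Keep AUC0-tau(6h),SS for the accumulation ratio. Do not set it against the AUCtau,ss in Protocol 1.4.1 or use it for clearance, because it covers only the first 6 h of a 6 h/18 h regimen.
4. Base steady-state ibudilast CL/F on AUC0-12h,SS, interpolating between 10 h and 24 h for the first 4 patients (an effect of about 0.4%). Note that it modestly overstates CL/F, without writing 9-15% into the SAP as fact. Define Vz/F = (CL/F)/lambda-z, and use one lambda-z window, excluding Day 28, for all patients summarised together.

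**Cost.** Definitions, row labels and footnotes; no new samples, visits or assays. The downsides are a slightly biased clearance and, if the common window ends at 24 h, a half-life that may be shorter than the terminal one and should be labelled so.

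**Separately,** Protocol Appendix 1 footnote c gives a morning and an afternoon dose at the Day 14 visit, while the synopsis, Section 4.4.2, Table 2 and the SAP state a morning dose only. These passages contradict each other and must be reconciled, since every Day 14 parameter is anchored on the last dose.
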